Sarcopenia is expected to be a major healthcare problem in the upcoming years in Europe(17), so, in response to this claim for Public Health Action, the European Union Geriatric Medicine Society founded the Special Interest Group (SIG) on sarcopenia that has taken the lead of bridging the gaps between clinical and research(18) in sarcopenia field(18), in line with the Conference on Frailty and Sarcopenia Research Task Force(7), and the World Health Organization's strategies to promote Optimal Aging(19). This goal of SIG on sarcopenia by EuGMS is being carried out by promotion of collaboration among International scientific societies and institutions; they have recently launched the Revised European consensus on definition and diagnosis (EWGSOP2)(4), the SARCUS project on ultrasound for sarcopenia

assessment in European countries(20)(21), and the first International Registry of patients with sarcopenia(22).

The new goal, assumed by the SIG on Sarcopenia is to assess sarcopenia in acute healthcare settings across European countries. This challenging project has been developed involving The European Academy for Medicine of Ageing (EAMA) is a postdoctoral fellowship on behalf of the EuGMS formed by European specialists in Geriatric Medicine focused on improving networking, establishing specific fields of interest, and providing an opportunity for lifelong learning(23). The Sarcopenia 9+ EAMA project working group has assumed the goals stablished by SIG on Sarcopenia by EuGMS and is focused on sarcopenia in acute healthcare settings across European countries.

Our study aims to provide an overview of sarcopenia assessment in hospitalized older patients across 9 European countries and has 5 objectives:

- 1. To determine prevalence of sarcopenia among hospitalized patients in Europe.
- 2. To determine incidence of sarcopenia during the hospital stay.
- To identify risk factors for the development of sarcopenia at the time of admission and during hospitalization (i.e. malnutrition as defined by the Global Leadership initiative on Malnutrition).
- 4. To assess sarcopenia as a risk factor for clinical adverse outcomes during hospitalization (hospital-acquired infections, falls, delirium, longer length-of-stay, disability, and mortality).
- 5. To assess sarcopenia as a risk factor for clinical adverse outcomes post-discharge (institutionalization, hospitalizations, falls, disability, and mortality) at 3- and 12-month follow-up.

METHODS

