Design: Longitudinal, prospective, observational multicenter study in consecutive hospitalized patients in 9 European countries [Belgium, Czech Republic, Denmark, Germany, Italy, Poland, Portugal, Spain, and United Kingdom]. The guidelines of the Strengthening the Reporting of Observational Studies in Epidemiology (STROBE) Statement will be followed(24). No major changes to methods or eligibility criteria after study commencement are planned.

Settings: Acute-care geriatric units. The description of the 9 settings involved in data collection has been stated in the affiliation section.

Participants: Patients aged 70 years and older who are admitted to the acute care geriatric units will be included. This may include acute medical conditions or chronic disease decompensation; patients are eligible for referral to acute geriatric units due to medical diseases, such us urinary tract infections, respiratory tract infections, pneumonia, coronary heart diseases, atrial fibrillation, congestive heart failure, stroke, delirium, electrolyte disturbances, kidney disease, cancer, etc... Exclusion criteria: Length of stay less than 24 h expected, inability to perform hand-grip, hip or lower limbs fractures, amputations, terminally ill patients admitted for palliative care, and unwillingness to take part in the study.

Main outcome measure: 1) Prevalence of sarcopenia at admission (± 48h). A prevalent case of sarcopenia will be considered if a patient fulfills the EWGSOP2 at admission; 2) Incidence of sarcopenia between admission and discharge (± 24h). A incident case of sarcopenia will be considered if a patient that do not fulfill EWGSOP2 diagnostic criteria at admission, fulfills the diagnostic criteria at discharge (diagnosis will be considered as a dichotomous variable -yes/no-); 3) Risk factors involved in the

development of sarcopenia during hospitalization; 4) Clinical adverse outcomes related to sarcopenia (incidence of hospital-acquired infections, falls, delirium, length-of-stay, disability, and mortality); 5) Clinical adverse outcomes post-discharge (institutionalization, hospital readmissions, falls, disability, and mortality) at 3- and 12-month follow-up.

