Statistical analysis: Descriptive analysis of the sample will use percentages and frequency distributions for categorical variables, and means with standard deviations (SD) or medians with interquartile ranges (IQR) for continuous variables. Univariate analysis will be used to check clinical and functional characteristics of the study participants according to the diagnosis of sarcopenia as defined by EWGSOP. Categorical variables will be compared by Chi-square or Fisher exact test, as appropriate, and continuous variables by Student t test. Univariate and multivariate analyses will be performed for all outcomes to examine possible associations with covariables. P values <0.05 will be considered as statistically significant. Statistical analysis will be performed using STATA 15.0 software (Stata Corp.; College Station, Texas, USA).

Sample size determination: Sample size was calculated in terms of the Sarcopenia 9+ EAMA project objectives; a sample size of 369 patients randomly selected will suffice to estimate with a 95% confidence and a precision ±5 percent units, a prevalence of sarcopenia at admission considered to be around 40%. For the incidence of sarcopenia study, a sample size of 218 patients randomly selected will suffice to estimate with a 95% confidence and a precision ±5 percent units, a population percentage considered to be around 15%. It has been anticipated a replacement rate of 10%; this relatively low percentage of loss reflects the expected adherence to usual care and follow-up of patients in a geriatric acute ward and a geriatric outpatient clinic for the duration of the study. Sample size calculation was performed using GRANMO

(Calculadora de Grandària Mostral GRANMO, version 7.12. Abril 2012, Institut Hospital del Mar d'Investigacions Mèdiques (IMIM), Barcelona, Spain)(45).

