Ethics: National and international research ethics guidelines will be followed(46), including the Deontological Code of Ethics, Declaration of Helsinki, and Spain's confidentiality law concerning personal data (Ley Orgánica 15/1999, 13 December, Protección de Datos de Carácter Personal). Detailed, understandable oral and written information will be provided to patients and family members (see file attached, Information file, including and in concordance with the General Data Protection Regulation (GDPR), informed consent to participate will be signed (see file attached, **Informed consent**). The study has been approved by Parc Salut Mar, Local Ethics Committee, Barcelona (CEIm - Parc Salut Mar, ref. number. 2018/8355/I), CHU Brugmann, Brussels (CE 2019/26), Krakow University Hospital, Krakow, and Centro Hospitalar Universitario de Lisboa, Lisbon (Processo n.º596/2018), and is currently submitted and pending of approval in the rest of centers. Data will be entered are treated in accordance with the provisions of the applicable data protection law in Spain and the General Data Protection Regulation (GDPR) (EU) nº 2016/679 of the European Parliament and Council, dated the 27 April of 2016, which entered into force last 25 May 2018.

Possible points for the discussion section

This is a protocol for a study to determine the prevalence and incidence of sarcopenia, to assess the factors involved in its onset and its clinical adverse outcomes during hospitalization in acute care and post discharge in a 3 and 12-month follow-up in in Europe; no data are yet available. The overall purpose of our study and is to take a

pragmatic approach in assessing sarcopenia in clinical practice in Europe and provide insight to develop eventual therapeutic interventions.

To date, few studies have addressed sarcopenia in hospitalized patients and no data are available across Europe. Following the model of the multicentre GLISTEN study, which assessed sarcopenia in acute geriatric care settings across Italy(13)(14), our survey will assess the prevalence, incidence, risk factors, and clinical outcomes of sarcopenia in hospitalized patients in 9 European countries. One of the limitations of our study will be the assessment of sarcopenia at discharge, mainly due to three issues.

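### The ±5-point precision assumes randomly selected, independent patients; for inference beyond the nine participating units it depends on an intraclass correlation that the plan does not give

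*Combined protocol and SAP*

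**What the plan says.** Under Sample size determination, the plan states for prevalence that "a sample size of 369 patients randomly selected will suffice to estimate with a 95% confidence and a precision ±5 percent units", at an expected prevalence of about 40%. For incidence, "a sample size of 218 patients randomly selected will suffice" for the same precision at about 15%. It adds: "It has been anticipated a replacement rate of 10" per cent. No design effect or ICC appears.

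The Design paragraph describes an "observational multicenter study in consecutive hospitalized patients in 9 European countries". Under Chronogram and dynamics, each partner aims for about 100 patients, with at least 50 if possible and no maximum. A team may go on recruiting until the slowest has finished, and a partner may fail to complete field work.

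Objective 1 reads "To determine prevalence of sarcopenia among hospitalized patients in Europe". The sentence introducing the objectives speaks of an "overview of sarcopenia assessment in hospitalized older patients across 9 European countries", and the discussion section of "clinical outcomes of sarcopenia in hospitalized patients in 9 European countries".

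The Statistical analysis paragraph plans percentages, standard two-group tests and this: "Univariate and multivariate analyses will be performed for all outcomes to examine possible associations with covariables". It names no confidence-interval method, centre weighting or centre term.

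**The concern.** The precision formula treats each patient as an independent draw from the target population. Patients in one unit share its admission policy, case mix and assessors, so their sarcopenia status may be correlated. The nine units belong to the project partners and are not described as a random sample of units. If the result is to speak for nine countries or for Europe, differences between units add sampling error that more patients per unit cannot remove. A plain binomial interval would then be too narrow for objectives 1 and 2.

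Objectives 3 to 5 raise a related issue. The discussion section says that length of stay and discharge procedures differ by country, and that the meaning of institutionalization may differ. Length of stay and institutionalization are study outcomes. If sarcopenia prevalence also varies by country, associations estimated without centre can be confounded.

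**Working it through.** **Inputs from the documents.** Prevalence p = 0.40, incidence p = 0.15, half-width d = 0.05, 95% confidence, replacement rate 10% (Sample size determination); nine settings (Settings); about 100 or at least 50 patients per partner (Chronogram and dynamics). Nine equal centres give N = 900 or N = 450. These are scenarios, not planned bounds.

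**Assumed.** ICC 0.01 to 0.05, because the documents give none.

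**1. The plan's own figures.** n = z²·p(1−p)/d².
- Prevalence: 1.96² × 0.24 / 0.0025 = 368.8, so 369.
- Incidence: 1.96² × 0.1275 / 0.0025 = 195.9, so 196; 196/0.9 = 217.8, so 218.

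Both reproduce. The 10% is built into 218 but not into 369 (369/0.9 = 410), although the text gives the rate after both.

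**2. The nine units as the target (fixed strata).** Half-width = 1.96·√(0.24/N): ±4.5 at 450 and ±3.2 at 900. The claim holds.

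**3. Beyond the nine units.** Design effect DE = 1 + (m − 1)·ICC with m = N/9; half-width = q·√(p(1−p)·DE/N). The plan's normal quantile is q = 1.96; t on 8 df gives q = 2.306.

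| Prevalence 40%, equal centres | ICC 0.01 | ICC 0.02 | ICC 0.05 |
|---|---|---|---|
| N = 450, normal | ±5.5 | ±6.4 | ±8.4 |
| N = 900, normal | ±4.5 | ±5.5 | ±7.8 |
| N = 450, t on 8 df | ±6.5 | ±7.5 | ±9.9 |
| N = 900, t on 8 df | ±5.3 | ±6.5 | ±9.2 |

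Example: N = 450, ICC 0.01: DE = 1 + 49 × 0.01 = 1.49; 1.96 × √(0.24 × 1.49/450) = 0.055.

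**4. Largest ICC compatible with ±5 (normal quantile).** ICC = (N/368.8 − 1)/(m − 1).
- N = 369 (m = 41): 0 in practice.
- N = 450: (1.2202 − 1)/49 = 0.0045.
- N = 900: (2.4405 − 1)/99 = 0.0146.
- As m grows without limit: 9/368.8 = 0.024. Above this, no recruitment in nine units reaches ±5.

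**5. Incidence.** If 60% are free of sarcopenia at admission and 10% are lost, 450 × 0.6 × 0.9 = 243 and 900 × 0.6 × 0.9 = 486 are at risk. With the normal quantile and ICC 0.01 to 0.05, the half-width is ±5.0 to ±6.8 at 243 and ±3.9 to ±6.1 at 486.

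**6. Unequal centres.** For crude pooling, replace m by Σm²/Σm. An illustrative 8×50 + 1×300 (N = 700) gives (8 × 2,500 + 90,000)/700 = 157.1. The normal half-width is then ±5.8 at ICC 0.01 and ±10.8 at 0.05, worse than nine equal centres of 50 despite 250 more patients.

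**7. Coverage.** Simulation with beta-binomial counts, p = 0.40, 40,000 draws, ICC 0.01 to 0.05:
- Plain binomial interval, equal centres: about 89% down to 70% (9×50) and 84% down to 58% (9×100).
- Cluster interval, equal centres: about 91% with the normal quantile, about 95% with t on 8 df.
- 8×50 + 1×300: a t (8 df) cluster interval on the crude percentage covers about 89% to 90%; the equal-centre-weight mean with t on 8 df covers about 95%.

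**The case against.** The strongest reply is that the shortfall is conditional. The documents give no ICC, the 0.01 to 0.05 range is an assumption, and the expected recruitment of about 900 is well above 369. At 900 the plan's own formula keeps ±5 up to an ICC of about 0.0146. If only the nine units are the target, there is no shortfall. All of this stands, and it limits the point to a claim that is not assured rather than one shown to fail.

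Several stronger readings are not supported:
- **The plan is short even without clustering.** With t on 8 df and ICC 0, the half-width at 450 is ±5.3. That comes from the choice of quantile; the plan's normal formula gives ±4.5.
- **The target population is undefined.** Age, unit type, countries and exclusions are all stated, and the mention of Europe in objective 1 can be read as shorthand for the nine countries. What is missing is how far inference is meant to extend, which is a minor matter of wording.
- **Crude pooling is wrong.** A patient-level percentage is a legitimate quantity. Equal centre weights represent neither countries nor patient volumes, so the choice is a preference.
- **Centre is left out of the models, so the associations are confounded.** The plan lists no model covariates for any outcome. Centre is unspecified, not excluded, and confounding is a risk that the documents do not demonstrate.

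The common discharge definition under Procedure and the limitations disclosed in the discussion section reduce the problem. The discussion itself concedes that discharge criteria may still differ, and no analysis is tied to that.

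**Conclusion.** The point holds in limited form. The figures 369 and 218 are not miscalculated; their assumption of independent random selection does not match the design. For the participating units ±5 is met. For the nine countries or Europe it depends on an unstated ICC: none can be tolerated at 369 patients, about 0.0045 at 450, about 0.0146 at 900, and above about 0.024 the target is out of reach with nine units. Within the assumed ICC range the prevalence half-width lies between ±4.5 and ±8.4 with the normal quantile, and between ±5.3 and ±9.9 with t on 8 df. These are equal-centre values; crude pooling of unequal centres does worse. Confidence is high that assumption and design differ and that the plan does not deal with it, but not in the size of the loss. No interval addresses the non-random choice of units.

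**What to change.** 1. **Sample size determination.** State that ±5 assumes simple random sampling. Then either limit the precision claim and the conclusion to the participating units, or give the expected half-width over a stated ICC range, labelled as an assumption for equal centres.
2. **Statistical analysis, objectives 1 and 2.** Report prevalence and incidence per centre together with the crude pooled figure. If inference goes beyond the units, give the 95% interval for the equal-centre-weight mean with t on completing centres minus 1 df, or use a small-sample-corrected interval for the crude figure. A plain t cluster interval on the crude figure is not enough when one unit is much larger. State that no interval covers how the units were chosen.
3. **Statistical analysis, objectives 3 to 5.** Include centre in the multivariate models as a random intercept, or use a conditional or penalised model where events are sparse. At 243 at risk, 243 × 0.15 is about 36 incident cases, or about four per centre.

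Cost: wording and modest extra analysis, with no extra patients. The stated precision becomes less favourable or the conclusion narrower, and models with few events lose some precision.

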Procedure (Table 2). Patients will receive a comprehensive geriatric assessment by an interdisciplinary team and a care plan for their specific needs, as part of the usual care in acute wards at admission. Tests for the diagnosis of sarcopenia will be performed within 48h of hospital admission, and again at discharge (± 24h) by the interdisciplinary team involved in this study. Discharge will be defined as the moment when the patient leaves the acute care hospital independently of their destination, to ensure coherence among countries in despite of the different healthcare resources (home back to Primary care, hospital-at-home scheme, care home (residential or nursing), postacute, transitional or rehabilitation care, transferred to another acute ward); all patients will be discharged according to clinical criteria as part of usual care of the unit, independently of the diagnosis of sarcopenia. Sarcopenia (outcome measure variable) will be assessed using EWGSOP 2 criteria and recorded at admission and at discharge. SARC-F questionnaire will be administered at admission and at 3- and 12- month follow-up. Blood samples will be extracted at admission by a trained member (usually a nurse) of the interdisciplinary team.

Hospital admission. Demographic data (age, date of birth, sex, marital status, living conditions, education level), administrative data (time of admission, number of previous hospital admissions in the last month and in the last 3 months), prevalent and incident medical conditions (Charlson index), diagnosis for hospital admission, hypertension assessment, medication use (Anatomical Therapeutic Chemical (ATC) Classification System, functional (Barthel index), nutritional (MNA-SF, weight, height, diagnosis of malnutrition as defined by GLIM), frailty (FRAIL and Frailty phenotype), and cognitive assessment (MMSE, GDS15, CAM), and pain (PI-NRS) will be collected within 48h of admission. Hospital discharge. Administrative data (time of discharge and place of discharge), medication use, weight, functional status, in-hospital adverse

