outcomes (urinary and respiratory tract infections, falls, and delirium), presence of pain (PI-NRS), days of fasting and bed rest, hypertension and orthostatic hypotension assessment, and mortality will be addressed within 24h prior to hospital discharge. **Follow-up.** Administrative data (date of the follow-up, hospital re-admissions, and visits to the emergency department), SARC-F questionnaire), pain (PI-NRS), functional status (Barthel index), institutionalization, hospital readmissions, and mortality after discharge will be assessed and collected by telephone interview with the patient or caregiver or from medical records at 3-month and 12 month-follow-up.

Chronogram and dynamics (Table 3): Email will be used for communications among the working group members. All the EAMA working groups have approved the study protocol. The approval of the Ethics Committees of all settings will be requested in all centers. Field work and data collection will start as soon each partner will obtained their respective Ethics Committee approval. Each partner will collect data during 4 months or the time needed to assess approximately 100 patients; however, every team may continue collecting data until the last team has finished the field work, if they choose to do so. A minimum of 50 patients should be collected by each partner, if possible, and no upper limit will be imposed. If one of the working group members is unable to complete the field work, collaboration in other tasks will remain an option. Data collection will be recorded in an Excel spreadsheet and analysed by the groups from Belgium, Germany, Italy, Spain, Poland, and United Kingdom.

Sources of funding: No external funding is anticipated. Every member of the working will use their own human and technical resources to develop the different phases of the study. The working group may seek eventual sources of funding (ERC, ESPEN grant fellowship, Erasmus+ Teaching, National grants, Fondo Investigación en

Salud Carlos III in Spain...) depending on the results of the ongoing project in further stages.

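### Should the prevalence sample size of 369 also carry the 10% allowance for loss that is built into the incidence size of 218?

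*Combined protocol and SAP*

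**What the plan says.** All the figures are in the Sample size determination section of the combined protocol and SAP.

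- Prevalence: "a sample size of 369 patients randomly selected will suffice to estimate with a 95% confidence and a precision ±5 percent units", for "a prevalence of sarcopenia at admission considered to be around 40" per cent.
- Incidence: "a sample size of 218 patients randomly selected will suffice", at the same confidence and precision, for an expected 15%.
- Loss: "It has been anticipated a replacement rate of 10" per cent. The sentence comes straight after the incidence figure and names neither size. Its reason is that "this relatively low percentage of loss reflects the expected adherence to usual care and follow-up of patients", on the ward and in the outpatient clinic.

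Three other sections bear on how these should be read. The Procedure section says: "Tests for the diagnosis of sarcopenia will be performed within 48h of hospital admission, and again at discharge". The Main outcome measure section defines prevalence from the admission assessment alone, and an incident case as a patient who does not meet the criteria at admission but does at discharge. The Chronogram and dynamics section sets recruitment by partner: about 100 patients each, no upper limit, and "A minimum of 50 patients should be collected by each partner, if possible".

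**The concern.** The two sizes are presented in parallel wording, and one unrestricted loss rate follows them. A reader would expect the rate to be in both figures or in neither. It is in only one, so the printed numbers count different things: 369 is a number to analyse, while 218 is a number before loss.

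If the 10% was meant for both and a team stopped at 369, the first main outcome would fall short of its stated precision. The reason given for the rate adds to the doubt. It mentions outpatient follow-up, whereas incidence is complete at discharge, so it does not clearly describe loss between the two in-hospital assessments.

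**Working it through.** **Inputs** (Sample size determination): z = 1.96 for 95% two-sided confidence; half-width d = 0.05; p = 0.40 for prevalence and 0.15 for incidence; loss 0.10. From Chronogram and dynamics: 50 to about 100 patients for each of nine partners.

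**Reproducing the plan's figures**, with n = z²p(1−p)/d²:

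- Prevalence: 1.96² × 0.40 × 0.60 / 0.05² = 368.8, so 369. This is the printed figure, with no allowance.
- Incidence: 1.96² × 0.15 × 0.85 / 0.05² = 195.9, so 196. Then 196/0.9 = 217.8, so 218, the printed figure. Multiplying instead gives 196 × 1.1 = 215.6, so 216, which does not match.

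| Convention | Prevalence | Incidence |
|---|---|---|
| No allowance | **369** | 196 |
| Divide by 0.9 | 410 | **218** |
| Multiply by 1.1 | 406 | 216 |

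No row gives both printed numbers. A one-sided z (260 and 138), a continuity correction (389 and 216) and a Wilson interval (366 and 196) do not give both either.

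**If the 10% belongs to incidence only.** Both figures are correct. The 218 must then be patients free of sarcopenia at admission, since only they can become incident cases. At 40% prevalence this needs 218/0.6 = 363.3, so 364 enrolled. Enrolling 369 gives 369 × 0.6 = 221 at risk and 221 × 0.9 = 199 assessed at discharge, above the required 196. So 369 enrolled serves both aims.

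**If the 10% belongs to both.** The consistent prevalence size is 369/0.9 = 410, which is 41 more. Half-widths at p = 0.40, from 1.96 × √(0.24/n):

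| Enrolled | After 10% loss | Half-width (points) |
|---|---|---|
| 369 | 332 | ±5.27 |
| 400 (eight partners × 50) | 360 | ±5.06 |
| 450 (nine × 50) | 405 | ±4.77 |
| 900 (nine × 100) | 810 | ±3.37 |

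The recruitment section counts patients assessed or collected. For a measure taken at admission, such patients are arguably evaluable already. Without the deduction, eight partners at 50 give n = 400 and ±4.80.

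**The case for a change.** The best case for a change is that the text never limits the 10% to incidence, and that its reason, with its reference to outpatient care, does not single out the interval from admission to discharge. The recruitment margin is also not guaranteed. The minimum of 50 per partner applies only where possible, the plan foresees that a partner may not complete field work, and the Ethics section names four approvals with the others pending. A clarifying clause would cost almost nothing.

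The first point stands as a remark on wording. It does not show that 369 is wrong. Outpatient follow-up comes after discharge, so it gives no better reason to inflate a prevalence measured at admission. Loss at that single assessment should also be limited: the eligibility criteria exclude patients who cannot perform hand-grip or do not wish to take part, and patients who cannot walk are assigned a gait speed of zero.

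The second point concerns recruitment rather than the allowance. The choice between 369 and 410 matters only if final enrolment lies between those numbers and a tenth of admission assessments are also lost. Below 369 both targets are missed; from 410 both are met.

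Nor is it harmless to print 410 and 218 together as two enrolment numbers. Enrolling 218 in all would leave 218 × 0.6 × 0.9 = 118 patients for incidence, and 1.96 × √(0.1275/118) gives ±6.4 points.

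**Conclusion.** The observation is accurate: the 10% is in 218 and not in 369, and the section does not say why. It is a gap in wording that a reader can fill sensibly. The outcome measured twice is inflated, the outcome measured once is not, and the loss sentence sits next to the former. On that reading there is no shortfall.

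On the other reading the worst case is ±5.27 instead of ±5.00 points, and it requires recruitment to stop at 369, which the plan nowhere proposes. At the planned 450 to 900 the stated precision holds either way. The one exception examined, eight partners at 50 with a further 10% removed, gives ±5.06, a negligible difference for a prevalence put at around 40%.

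This rests on the plan's own assumptions (40%, 15%, 10% and simple random sampling) and on partners reaching about 50 patients each. The incidence-only reading is an inference from the order of the sentences and the timing of the assessments; the document does not state it. No estimate, analysis or recruitment target would change if it were spelled out.
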